# Sample Size Estimation

Our Aim 1 outcome is compliance with swabbing at both baseline and 12 months. We will compare study arms using a Mantel-Haenszel test for difference in proportions in a stratified design. Assuming a large sample size in each arm (~200), we can approximate a lower bound for our

power assuming a chi-squared distribution with 1 degree of freedom. Given swab return data in cross-sectional studies, we anticipate ~80% of persons will return the home-based swab at baseline. Me estimate 10% loss to follow up at 12 months (n=180) and 80% of persons will return a home-collected swab (144) for 72% compliance at 12 months (i.e., 144/200).

Table 1. Power to detect difference in proportion of DNA samples received: home-based vs. clinic-based											
Proportion of home samples	Proportion of clinic samples	Difference	Power								
0.63	0.43	0.20	0.89								
0.72	0.54	0.18	0.84								
0.70	0.56	0.14	0.63								
0.65	0.52	0.13	0.55								

Using the same algorithm with cervical cancer screening compliance data,  $^{80}$  we estimate 70% of clinic-based attendees at baseline and 60% at 12 months also with 10% loss to follow up (200\*0.9 = 180; 180\*0.60 = 108 or 108/200 = 54% compliance). Using intent to treat, if 144 home-collected swabs (72%) and 108 clinic-collected swabs (54%) are returned at 12 months, and assuming two-sided tests and alpha of 0.05, we have 84% power to detect a difference (0.18) between arms (table 1) for Aim 1. Power was computed with PASS 14.

Aim 1 is the primary driver of the sample size of 400 which also provides ample power for assessing factors associated with compliance in Aim 2 as shown in table 2.

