#### PARTICIPANT RANDOMIZATION

Persons officially enrolled will be randomized in a 1:1 allocation to either the home- or clinic-based swabbing. Blocked randomization is not necessary due to sample size. The Houston Data Coordinating Center will prepare randomization lists using Stata Version 13 (College Station, TX). The randomization process will occur for a consented participant who has satisfactorily completed the baseline CASI. Given obvious differences of each arm, randomization cannot be blinded to study staff or participants although participant data including study arm will be blinded to lab staff.

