# Computer-Assisted Self-Interviews

To accomplish the Aim 2 objective, to assess factors independently associated with MSM and transpersons who return a swab at baseline and 12 months, we will design CASI questionnaires capturing demographics, attitudes, and behavioral data in the baseline survey, after the 0- and 12-month swabbing time points, and after HRA. All participants will complete CASIs in English or Spanish (after translation and back translation) on the HIPAA-compliant secure web platform REDCap (Vanderbilt University). Each CASI will include questions adapted from validated cervical cancer screening survey. For adaptation, the items were modified with the input of co-Investigators, study staff and cognitive interviews with the target community. The surveys have subscales that can be used independently if any of the psychometric properties of the subscale indicate that it is not a reliable or valid measure of the construct. Since participants will complete CASIs in the study spanning the time from baseline CASI to post-HRA CASI, changes in participants' attitudes to swabbing or HRA will be captured.

The baseline survey conducted remotely after consenting will record demographics of the study entry population including anal cancer anxiety, prior experience with anal cancer, prior experience with other anal diseases, self-sampling acceptability, prior anal cancer screening (including HRA), benefits/barriers of anal cancer screening, and sexual behavior.

Participants will complete another CASI after each swabbing. Participants will be asked about the experience of self-sampling/clinician sampling and DARE within the framework of HBM constructs. 44,71 Experience with DARE will be asked of Arm 1 participants at the end of their clinic DARE visit. Other CASI items will cover kit mailing, kit return, kit appearance, kit materials, and trust in the clinician (depending on study arm). The CASIs will include anxiety-related questions about anal cancer screening and the annual screening interval.

Participants will complete a final short CASI to assess the acceptability of HRA like perceived barriers (embarrassment) in addition to prior anoscopy experiences, the perception of pain, and knowledge of HRA availability.

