#### EPIDEMIOLOGICAL AND STATISTICAL CONSIDERATIONS

#### Analysis

Participants will be randomized to either Arm 1 or Arm 2. For Aim 1 our primary analysis is to compare the proportion of those who comply with 0 and 12-month swabbing in the home- and clinic-based arms. Our primary endpoint, compliance, is categorized as "Yes" if a swab is returned at 0 and 12 months and "No" otherwise. The null hypothesis is that the proportion of those complying in each arm is the same. Under the intention-to-treat principle, all participants who are randomized are included in the analyses (primary and exploratory). We will compare the proportion of persons who are compliant in the two arms using a Mantel-Haenszel test for difference in proportions in a stratified design ( $\alpha$ =0.05). For sensitivity analysis we will also do a per protocol analysis comprised of compliant participants.

Participants will be considered non-compliant for either baseline or 12-month swab if they do not provide a swab within 30 days after kit mailing or clinic appointment. Persons randomized to arm 1 who "crossover" and attend a doctor's visit for anal cancer screening, including DNA collection, without returning a home-base kit, will be counted as non-compliant.

For Aim 2, to determine factors associated with compliance, we will use purposeful modeling strategies. We will perform a bivariate logistic regression for each factor, and those factors with a p-value less than 0.25 in the bivariate analysis will be included in a multivariable logistic regression model. Given that we expect 144 and 108 12-month swabs returned from arm 1 and arm 2, respectively, we can safely examine up to 10 factors simultaneously in the model and maintain the recommended minimum of 10 events per variable in the multivariable model. We will pay particular attention to the aforementioned HBM constructs, e.g., self-efficacy, to ascertain their ability to explain variance in compliance. Associations in the multivariable model will be considered significant with a p-value of <0.05. Adjusted and unadjusted odds ratios will be

reported with 95% CIs. We will regress compliance on covariates after adjusting for study arm, HIV status, race, and age (i.e., the randomization strata) and potential confounders identified with Directed Acyclic Graphs including insurance status, socioeconomic status and ethnicity.

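### The Aim 1 comparison omits prior-screening and attitude measures collected before randomisation and does not name its strata; the cost is modest precision, not validity

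*Combined protocol and SAP*

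**What the plan says.** **Endpoint and test.** Under Analysis, compliance "is categorized as 'Yes' if a swab is returned at 0 and 12 months and 'No' otherwise". The arms are compared "using a Mantel-Haenszel test for difference in proportions in a stratified design" at a 0.05 level, and Sample Size Estimation repeats this: "We will compare study arms using a Mantel-Haenszel test for difference in proportions", again in a stratified design. Power is approximated by a 1-df chi-square, offered as a lower bound: "assuming two-sided tests and alpha of 0.05, we have 84% power to detect a difference (0.18) between arms".

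**Strata.** Neither statement of the primary test says what the strata are. The only list is in the Aim 2 paragraph of Analysis, which speaks of "adjusting for study arm, HIV status, race, and age (i.e., the randomization strata". Participant Randomization describes 1:1 allocation, says "Blocked randomization is not necessary due to sample size", and mentions no strata.

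**Baseline data.** Participant Randomization says "The randomization process will occur for a consented participant who has satisfactorily completed the baseline CASI". Computer-Assisted Self-Interviews lists, besides demographics and other items, "self-sampling acceptability, prior anal cancer screening (including HRA), benefits/barriers of anal cancer screening, and sexual behavior". Under Eligibility Survey, Consenting and Enrollment Procedures, only selected questions must be completed for enrolment.

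**Use of these data.** They feed Aim 2: factors are screened at p<0.25, entered in a multivariable logistic model that also contains study arm, and reported as odds ratios. No covariate-adjusted arm comparison is specified for Aim 1.

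**The concern.** Variables measured before allocation cannot be affected by the arm. Adjusting the primary contrast for those that predict compliance therefore targets the same quantity, the difference in compliance proportions, with a smaller variance and a correction for chance imbalance. The sponsor expects such predictors to exist: Background expects HIV status to influence actual compliance, and Aim 2 looks to Health Belief Model constructs to explain it.

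A Mantel-Haenszel test can carry a few categorical factors. It cannot use an acceptability or barriers score without cutting it into categories, and the only strata named anywhere (HIV status, race, age) leave out attitudes and prior screening. At stake is a wider interval than the data could give, and some loss of power if the true difference is nearer the lower rows of Table 1 than the planned 0.18.

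**Working it through.** **1. The plan's own power figures.** Inputs from Sample Size Estimation: about 200 per arm, two-sided alpha 0.05. With pooled variance under the null,

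power = Φ[(d − 1.96·√(2·p̄(1−p̄)/n)) / √((p1(1−p1)+p2(1−p2))/n)].

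- 0.72 v 0.54, n = 200: p̄ = 0.63. Null SE = √(0.4662/200) = 0.0483; alternative SE = √(0.4500/200) = 0.0474. Power = Φ[(0.18 − 0.0946)/0.0474] = Φ(1.80) = 0.964. Printed: 0.84.
- 0.65 v 0.52, n = 200: p̄ = 0.585. Null SE = √(0.48555/200) = 0.0493; alternative SE = √(0.4771/200) = 0.0488. Power = Φ[(0.13 − 0.0966)/0.0488] = Φ(0.68) = 0.753. Printed: 0.55.

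The printed values are not reproduced at 200 per arm. With n = 125 the same formula gives 0.891, 0.843, 0.632 and 0.551, matching all four rows of Table 1 (0.89, 0.84, 0.63, 0.55). That discrepancy is a separate matter, but it fixes the starting point: the gains below are measured from the recomputed values, not the printed ones.

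**2. Chance imbalance.** Under simple 1:1 allocation, a factor with 50% prevalence differs between arms by up to ±1.96·√(2·0.25/200) = ±0.098 (95% range). As an illustration, if that factor shifted compliance by an assumed 15 points, an imbalance at the edge of this range would move the observed arm difference by 0.098 × 0.15 = 0.015, or 1.5 points.

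**3. Gain against an unadjusted test.** Simulation: 400 people, independent 1:1 allocation, 3,000 trials per setting. Assumed predictors: one binary with 50% prevalence, one binary with 26% (the prior-screening rate reported in Background) and one continuous score. Strengths are assumptions, because the documents give none: weak / moderate / strong = binary OR 1.5 / 2.0 / 2.5 and per-SD OR 1.25 / 1.5 / 2.0. The adjusted estimate is the risk difference standardised from a logistic model, with an influence-function standard error.

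| | Weak | Moderate | Strong |
|---|---|---|---|
| Variance, adjusted/unadjusted | about 0.98 | about 0.93 | about 0.86 |
| Equivalent extra participants, 400/ratio − 400 | 8 | 30 | 65 |
| 95% CI half-width at 0.72 v 0.54 (unadjusted 1.96 × 0.0474 = 0.093), times √ratio | 0.092 | 0.090 | 0.086 |

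Repeat runs gave ratios between about 0.84 and 0.99, depending on the row of Table 1.

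**4. Gain against a stratified test.** Here the comparator is a Mantel-Haenszel test stratified on the two binary predictors. This is an assumption, since the plan's strata are not defined.

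| Power, Mantel-Haenszel → adjusted | Weak | Moderate | Strong |
|---|---|---|---|
| 0.72 v 0.54 | 0.965 → 0.968 | 0.967 → 0.973 | 0.972 → 0.985 |
| 0.65 v 0.52 | 0.748 → 0.757 | 0.766 → 0.786 | 0.788 → 0.836 |

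The gain is 0.3 to 1.3 points in the first row and 0.9 to 4.8 in the second. A repeat gave 0.2-1.3 and 0.6-4.5.

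**5. Type I error.** In these settings, null rejection was 0.053-0.055 for the unadjusted and Mantel-Haenszel tests and 0.044-0.060 for the adjusted test across runs. The simulation standard error is √(0.05·0.95/3000) = 0.004.

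**The case against.** The strongest reply is that the primary test is already stratified. If its strata are HIV status, race and age, it uses three baseline variables and corrects imbalance on them. That stands. A reader might infer that the primary analysis ignores all baseline information; the words about a stratified design do not support that. What can be said is that the strata are unnamed where the test is defined, that the randomisation section describes none, and that attitudes and prior screening are outside the only list given. If there are in fact no strata, step 3 is the relevant comparison; if there are, step 4 is closer.

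A reader might also infer that the unadjusted test is biased or has inflated error because imbalance is left uncorrected. It does not: the error rate already allows for chance imbalance. Adjusted rejection was at times slightly above nominal, so a one-point power gain is near the limit of what these simulations can show.

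Predictor strength is also uncertain. In the sponsor's earlier study, reported in Background, intention to swab annually did not differ by age, race, ethnicity, marital status or HIV status (95% v 97%), and 93% would use a home swab, so an acceptability score may sit near its ceiling. This stands as a caution. Background itself separates intention from behaviour, and weak predictors make the gain small rather than harmful.

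Finally, it would be wrong to assume that every randomised person supplies every item: only selected questions are compulsory, and Threats to Validity foresees imputing covariates. Any adjustment therefore needs a missing-data rule.

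**Conclusion.** The point holds as one of efficiency. Prior screening, acceptability and benefits/barriers are measured before randomisation and left out of the Aim 1 contrast, which uses at most a few unnamed categorical strata. For the assumed range of predictor strengths, adjustment lowers the variance of the arm difference by about 2-15% against an unadjusted test. Against a Mantel-Haenszel test on two binary predictors, it adds about 0-1 point of power at the planned 0.72 v 0.54 and about 1-5 points at 0.65 v 0.52.

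It would be tempting to present this as rescuing a trial with 84% or 55% power. The documents do not support that, because at the stated 200 per arm the starting values are about 0.96 and 0.75. At the planned difference the benefit is mainly a narrower interval and protection against an unlucky imbalance. All the sizes rest on assumed odds ratios, and with weak predictors the gain is close to nil.

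The Aim 2 model does not fill the gap. It contains study arm, but its covariates are selected from the data and it reports odds ratios, not a pre-specified difference in proportions.

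**What to change.** In Analysis and Sample Size Estimation:

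- Make the primary estimate the arm difference in compliance proportions, standardised from a logistic working model with arm and a short fixed list, with a robust standard error and 95% CI.
- Fix the list before the data are analysed: age, race, prior anal cancer screening, baseline self-sampling acceptability score, and HIV status as self-reported before randomisation. Verified HIV status should not be used, because under Medical Records anyone not confirmed positive from records is tested at the baseline clinic visit, after allocation.
- Draw the list from survey items required for enrolment, or state a simple rule for missing baseline values that does not depend on arm, so that everyone randomised stays in the analysis.
- Keep the Mantel-Haenszel test as the supporting analysis, name its strata, and reconcile the Aim 2 phrase about randomisation strata with Participant Randomization.

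A short list is supportable: on the plan's figures, 144 + 108 = 252 comply and 400 − 252 = 148 do not, so even the smaller group gives about 14 parameters at the plan's own ten events per variable.

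The cost is a few lines of text and some programming, with no new data. The downside is that the list and the missing-value rule must be settled in advance, for a gain that may be small.

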#### Swabbing 2 at 12 months and HRA Scheduling

Procedures for kits and clinic appointments at 12 months will mirror baseline procedures. All persons in arm 1 will be reminded 11.5 months after baseline of the shipment of kit #2 or if in arm 2, the need to schedule clinic appointment #2 for clinician-based swabbing. Reminders and communication to all participants will mirror procedures typically used by medical clinics, e.g., birthday greetings and up to four reminders. At the same time, all persons will be scheduled for HRA at the Froedtert/MCW Anal Dysplasia Program. We will make up to four attempts to schedule a person for HRA. For a person who declines the HRA, we will request the reason(s) why. Persons in both arms who are lost to follow up after consenting will still be solicited for a 12-month swabbing and HRA.

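### The sample size is justified with 12-month return rates (72% and 54%) rather than both-swab compliance, and the Table 1 power figures do not correspond to 200 per arm

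*Combined protocol and SAP*

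**What the plan says.** The Study Synopsis, the Analysis section and the Sample Size Estimation section agree on the endpoint. The last states: "Our Aim 1 outcome is compliance with swabbing at both baseline and 12 months". Under Analysis, a participant counts as compliant only "if a swab is returned at 0 and 12 months", and everyone randomized is analysed.

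The Sample Size Estimation section gives these inputs:

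- **Arm size:** "Assuming a large sample size in each arm (~200").
- **Home arm:** about 80% return at baseline, 10% loss to follow-up, then "80% of persons will return a home-collected swab (144) for 72% compliance at 12 months (i.e., 144/200").
- **Clinic arm:** "we estimate 70% of clinic-based attendees at baseline and 60% at 12 months also with 10% loss to follow up", which gives 108/200 = 54%.
- **Power:** "we have 84% power to detect a difference (0.18) between arms", two-sided at 0.05 and under intention to treat. Table 1 gives three further pairs of rates.

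Two other statements bear on the point. The Analysis section reuses the same counts for Aim 2: "Given that we expect 144 and 108 12-month swabs returned from arm 1 and arm 2, respectively". The section on the second swabbing says: "Persons in both arms who are lost to follow up after consenting will still be solicited for a 12-month swabbing and HRA".

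**The concern.** The figures called compliance in the power calculation are the proportions expected to return the 12-month swab. The baseline rates are stated but never enter the calculation. Because people lost after consenting are still asked for a 12-month swab, someone can be among the 144 or the 108 without a baseline swab, and that person fails the primary endpoint. The plan gives no both-swab rate and no assumption about how return at the two visits is related.

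In addition, the printed power values look too low for 200 per arm at the rates beside them.

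The numerical justification for 400 participants therefore describes a different quantity and a different arm size from those to be analysed. It may also affect the Synopsis hypothesis that most participants will comply, since expected overall compliance with both swabs is lower than the plan implies.

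**Working it through.** **Inputs (Sample Size Estimation).** Home arm: baseline 0.80; 12 months 0.90 × 0.80 = 0.72. Clinic arm: baseline 0.70; 12 months 0.90 × 0.60 = 0.54. Arm size 200, two-sided alpha 0.05, 1-df chi-squared.

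**Step 1: reproduce the printed power.** With p̄ the weighted mean rate,

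SE₀ = √[p̄(1−p̄)(1/n₁+1/n₂)], SE₁ = √[p₁(1−p₁)/n₁ + p₂(1−p₂)/n₂], power ≈ Φ[(|p₁−p₂| − 1.96·SE₀)/SE₁].

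For 72% vs 54% at 200 per arm, SE₀ = 0.0483 and SE₁ = 0.0474, so power = Φ[(0.18 − 0.0946)/0.0474] = 96.4%. At 144 and 108, SE₀ = 0.0610 and SE₁ = 0.0608, so power = Φ[(0.18 − 0.1195)/0.0608] = 84.0%.

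| Home vs clinic | Printed | 200/200 | 180/180 | 144/108 |
|---|---|---|---|---|
| 0.63 vs 0.43 | 0.89 | 0.982 | 0.970 | 0.888 |
| 0.72 vs 0.54 | 0.84 | 0.964 | 0.946 | 0.840 |
| 0.70 vs 0.56 | 0.63 | 0.829 | 0.788 | 0.630 |
| 0.65 vs 0.52 | 0.55 | 0.753 | 0.708 | 0.548 |

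Neither 200 nor 180 per arm fits. Arms of 144 and 108 fit every row. So does about 125 per arm (0.891, 0.843, 0.632, 0.551), but the plan states no such size. The likely explanation is that non-return was counted twice, once in the rates and again in the denominators.

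The choice of test does not explain the gap. For 72% vs 54% at 200 per arm, the continuity-corrected and Fisher exact calculations both give 95.5%.

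**Step 2: what the stated rates imply for both swabs.** P(both) lies between a + b − 1 and min(a, b), where a is the baseline rate and b the 12-month rate.

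- Home: 0.80 + 0.72 − 1 = 0.52, up to 0.72.
- Clinic: 0.70 + 0.54 − 1 = 0.24, up to 0.54.
- Overall: 38% to 63%.

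The planned rates are the upper ends, reached only if every 12-month returner also returned at baseline. Two intermediate cases, both assumptions:

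- Independence: 0.80 × 0.72 = 57.6%; 0.70 × 0.54 = 37.8%; overall 47.7%.
- All loss among baseline non-returners: 0.80 × 0.80 = 64%; 0.70 × 0.60 = 42%; overall 53%.

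**Step 3: power for both-swab compliance at 200 per arm.** With within-person correlation r, P(both) = ab + r√[a(1−a)b(1−b)]. The square root is 0.180 for home and 0.228 for clinic. The values of r are illustrative; the documents give none.

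| r home | r clinic | Home | Clinic | Power |
|---|---|---|---|---|
| 0 | 0 | 57.6% | 37.8% | 98.0% |
| 0.1 | 0.1 | 59.4% | 40.1% | 97.4% |
| 0.3 | 0.3 | 63.0% | 44.7% | 96.0% |
| 0.5 | 0.5 | 66.6% | 49.2% | 94.3% |
| 0 | 0.3 | 57.6% | 44.7% | 74% |
| 0 | 0.5 | 57.6% | 49.2% | 39% |
| 0.3 | 0 | 63.0% | 37.8% | over 99% |
| 0.5 | 0 | 66.6% | 37.8% | over 99% |

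Overall compliance reaches 50% at a common r of (0.50 − 0.477)/[(0.180 + 0.228)/2] = 0.11, or 0.13 if the correlation is taken among retained participants only.

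**Step 4: Aim 2 count.** Under independence there are 200 × (0.576 + 0.378) ≈ 191 compliers and 209 non-compliers. With 10 factors that is 191/10 = 19.1 per factor in the smaller class. At the upper bounds (252 compliers, 148 non-compliers) it is 14.8; at the lower bounds (152 compliers) it is 15.2. The 10-factor limit holds throughout.

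**The case against.** The strongest reply concerns weight. The denominator error makes stated power too low, so a sample of 400 exceeds its advertised power whenever dependence is similar in the two arms. That stands: this is not evidence of an underpowered trial.

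The plan also calls its power a lower bound, which 96% does not contradict. In context, however, that phrase refers to approximating the stratified Mantel-Haenszel test by a chi-squared test. It does not explain a value that fits arms of 144 and 108.

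Table 1 already includes smaller differences. Its last two rows (0.14 and 0.13) cover roughly the gap in the 74% case, with lower printed power, so only the 39% case goes beyond the table. That is fair, but the rows are not presented as both-swab rates and their power values are not for 200 per arm.

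No dependence in one arm and strong dependence in the other is a constructed case. That is also fair, and the mirror cases above exceed 99%. The unequal cases show sensitivity to something left unstated; they are not forecasts.

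The 72% could be read as baseline returners less 10% loss, since 0.80 × 0.90 = 0.72. The same reading gives 0.70 × 0.90 = 63% in the clinic arm, not 54%, so it fails.

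Finally, the 144/108 explanation is inferred. What is established is that 200 per arm does not give Table 1. The Aim 2 recount changes no conclusion, and the Analysis section specifies no test against 50%, so the majority point concerns expectations only.

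**Conclusion.** The concern holds on both counts. On the plan's own marginal rates, 72% and 54% are ceilings for the primary endpoint. The attainable ranges are 52–72% and 24–54%, and the plan does not say where in them it expects to be. At the stated 200 per arm, Table 1 should read 0.98, 0.96, 0.83 and 0.75 rather than 0.89, 0.84, 0.63 and 0.55.

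The two errors differ in effect: expected compliance is overstated unless every 12-month returner also returned at baseline, and power at the listed rates is understated. With equal correlation between 0 and 0.5 in both arms, power for the endpoint is 94–98%. It falls below the advertised 84% if the both-swab difference drops below about 0.14 to 0.15, which would need markedly stronger dependence in the clinic arm. These results rest on the plan's marginal rates, a pooled-variance two-proportion test and illustrative correlations. The figures should be corrected; the sample size need not change on this account.

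**What to change.** 1. In Sample Size Estimation, state the expected both-swab rate in each arm, the dependence assumption behind it, and the range (home 52–72%, clinic 24–54%; 57.6% and 37.8% under independence).
2. Recompute Table 1 and the power sentence for those rates at 200 per arm. Include cases with stronger dependence in the clinic arm and their mirror cases.
3. If the 72% vs 54% row is kept, label it as the full-overlap upper bound and give 96.4% in place of 84%, or state and justify the arm sizes used.
4. In the Aim 2 paragraph of the Analysis section, count both-swab compliers and non-compliers (about 191 and 209 under independence) instead of 12-month swabs. The 10-factor limit can stay.

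The cost is a correction to text and one table. No participants are added, and the endpoint and test are unchanged. Expected compliance will be quoted as a range, generally lower than now.

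### The stated 84% power for 72% vs 54% is about 96% at 200 per arm, and both rates are 12-month returns, so power for the both-swabs primary endpoint rests on joint rates the plan does not give

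*Combined protocol and SAP*

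**What the plan says.** Sample Size Estimation defines the outcome correctly: "Our Aim 1 outcome is compliance with swabbing at both baseline and 12 months". It then sets the frame for the power calculation, "Assuming a large sample size in each arm (~200), we can approximate a lower bound for our" power, using a chi-square with 1 degree of freedom, two-sided at 0.05.

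For the home arm, "we anticipate ~80% of persons will return the home-based swab at baseline". At 12 months, 10% loss leaves 180, of whom "80% of persons will return a home-collected swab (144) for 72% compliance at 12 months (i.e., 144/200"). For the clinic arm, "we estimate 70% of clinic-based attendees at baseline and 60% at 12 months", also with 10% loss, giving 108/200 = 54%. The result is "we have 84% power to detect a difference (0.18) between arms (table 1) for Aim 1".

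Table 1 is headed "Power to detect difference in proportion of DNA samples received" and lists four pairs of rates. The section closes with "Aim 1 is the primary driver of the sample size of 400 which also provides ample power" for Aim 2, which is shown in Table 2.

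Three other places matter. The Analysis section codes compliance as yes only if swabs come back at both time points, keeps everyone randomized in the denominator, and describes 144 and 108 as 12-month swabs. The section on the 12-month swab says that people lost after consent are still asked for that swab.

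**The concern.** There are two separate problems.

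- **The power figure.** A difference of 18 points near the middle of the scale, with 200 per arm, should have power well above 84%. If the printed value cannot be obtained from the printed inputs, either the inputs or the output of Table 1 are misreported.
- **The endpoint.** The rates entered are the proportions returning the second swab. The endpoint is the proportion returning both. The two agree only if nobody returns the second swab without the first, which the plan does not state.

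The plan names Aim 1 as what drives the 400, so this paragraph is the justification of the trial's size. As it stands, a reader can neither reproduce its main figure nor tell what both-swabs difference the trial can detect.

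**Working it through.** **Inputs** (Sample Size Estimation and Analysis): 200 per arm; two-sided alpha 0.05; 1-df chi-square; all randomized in the denominator. Home: baseline 0.80, 12-month 0.9 × 0.80 = 0.72. Clinic: baseline 0.70, 12-month 0.9 × 0.60 = 0.54. The 10% loss is already inside 0.72 and 0.54.

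**1. Trying to reproduce the 84%.** With n per arm and mean rate p̄, power = Φ(z), where

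z = [ |p₁ − p₂| − 1.96·√(2p̄(1−p̄)/n) ] / √( (p₁(1−p₁) + p₂(1−p₂))/n )

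For 0.72 and 0.54, p̄ = 0.63:

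- √(2 × 0.63 × 0.37 / 200) = 0.0483
- √((0.2016 + 0.2484) / 200) = 0.0474
- z = (0.18 − 1.96 × 0.0483) / 0.0474 = 1.80, so power = 0.964

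At 200 per arm, other forms of the test do not reach 84% either: unpooled 0.967, continuity-corrected 0.955, Fisher exact 0.955, alpha 0.01 0.880.

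**2. All rows of Table 1**

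| Home vs clinic | Printed | 200/200 | 180/180 | 125/125 | 144/108 |
|---|---|---|---|---|---|
| 0.63 vs 0.43 | 0.89 | 0.982 | 0.970 | 0.891 | 0.888 |
| 0.72 vs 0.54 | 0.84 | 0.964 | 0.946 | 0.843 | 0.840 |
| 0.70 vs 0.56 | 0.63 | 0.829 | 0.788 | 0.632 | 0.630 |
| 0.65 vs 0.52 | 0.55 | 0.753 | 0.708 | 0.551 | 0.548 |

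The printed column fits about 125 per arm, or arms of 144 and 108. The latter are the expected numbers of 12-month swabs, so non-return may have been counted twice. That is an inference, because the software inputs are not documented.

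**3. Table 2 as a control.** With 200 per arm, all twelve cells come out within 0.01 of print. For odds ratios 1.50, 1.75, 2.00 and 2.25 at exposure 0.4, the recomputed values are 0.520, 0.795, 0.932 and 0.981, against 0.52, 0.79, 0.93 and 0.98. The two tables therefore do not rest on the same sample size.

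**4. What 200 per arm detects.** From 54%: 14.0 points with power 0.82; 14.5 points with 0.85.

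**5. The both-swabs rate.** With baseline return a and 12-month return b, the joint rate lies between max(0, a + b − 1) and min(a, b).

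- Home: 0.80 + 0.72 − 1 = 0.52, up to 0.72
- Clinic: 0.70 + 0.54 − 1 = 0.24, up to 0.54

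So 72% and 54% are the top of each range.

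**6. Power for the endpoint at 200 per arm.** Every share and correlation below is an assumption; the documents give none. The first block varies the share of 12-month returners who also gave swab 1. The second uses joint rate = ab + r·√(a(1−a)b(1−b)), where the root is 0.180 for home and 0.228 for clinic.

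| Link assumed (home, clinic) | Both-swabs rates | Power |
|---|---|---|
| Share 100%, 100% | 72.0% vs 54.0% | 0.96 |
| Share 90%, 90% | 64.8% vs 48.6% | 0.91 |
| Share 95%, 100% | 68.4% vs 54.0% | 0.84 |
| Share 90%, 100% | 64.8% vs 54.0% | 0.60 |
| r = 0, 0 (independence) | 57.6% vs 37.8% | 0.98 |
| r = 0.4, 0.4 | 64.8% vs 46.9% | 0.95 |
| r = 0.71, 0.71 | 70.3% vs 54.0% | 0.92 |
| r = 0.2, 0.4 | 61.2% vs 46.9% | 0.82 |
| r = 0.2, 0.5 | 61.2% vs 49.2% | 0.67 |
| r = 0, 0.4 | 57.6% vs 46.9% | 0.57 |
| r = 0, 0.71 | 57.6% vs 54.0% | 0.11 |
| r = 0.4, 0 | 64.8% vs 37.8% | over 0.99 |

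Independence gives high power here, so it is a scenario and not a floor. What lowers power is a weaker link at home than in clinic.

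**The case against.** The best defence runs as follows. The arithmetic error is on the safe side: for every pair in Table 1, 400 participants give more power than printed, and a value offered as a lower bound is not false because the truth is higher. Table 1 already includes a lower pair, 63% vs 43%, close to the independence case. The low-power scenarios all need home 12-month returners to be less likely than clinic ones to have given swab 1, whereas the stated baseline returns (80% home, 70% clinic) point, if anything, the other way. With equal shares of 80% the rates are 57.6% vs 43.2% and power is about 0.82; with 90% home and 85% clinic they are 64.8% vs 45.9% and power is about 0.97. The primary analysis itself uses the right endpoint in everyone randomized, so the result will not depend on these planning rates.

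Much of this stands. The error does not threaten the design, the low figures are scenarios rather than forecasts, and the trial is not shown to be underpowered. Two parts do not stand. The lower-bound wording refers to replacing the stratified test by a 1-df chi-square at about 200 per arm, and that calculation is the one that gives 0.96. And although the text attaches the 0.18 row to Aim 1, it derives no both-swabs rate for that row or any other, so the 63% vs 43% row cannot be read as an allowance for the joint endpoint. Kit return and clinic attendance are different behaviours, so an equal link is itself an assumption that has to be stated.

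**Conclusion.** Both parts hold. For 72% vs 54% at 200 per arm the power is about 96%, not 84%, and all four rows of Table 1 are too low for that size. This rests only on the plan's own inputs.

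The same 72% and 54% are upper limits for the primary endpoint, reached only if every 12-month returner also gave the baseline swab. Power for the actual endpoint is about 92% to 98% when the within-person correlation is equal in both arms and between 0 and 0.71. It can fall to about 60% or lower when the link is weaker at home than in clinic, and exceeds 99% in some cases the other way. The plan gives nothing with which to choose among these.

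This should be corrected. It is a fault in the stated justification of the sample size, not evidence that 400 is too few.

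**What to change.** - Recompute Table 1 at 200 per arm (0.98, 0.96, 0.83, 0.75) and state the arm sizes behind each table.
- Replace 84% with about 96% for 72% vs 54%, stated as conditional on every 12-month returner having also returned the baseline swab.
- Add that 200 per arm detects about 14 to 14.5 points from 54% with 82% to 85% power.
- State the both-swabs rate assumed in each arm and the assumed link between the two returns, and label 72% and 54% as upper limits.
- Show power over a short range in which that link may differ by arm, including less favourable cases. Do not call independence a lower limit, or the sample size conservative in general.

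The cost is text, one table and a brief calculation. Some of the power values shown may be less favourable. The 400, the test and the procedures stay as they are.
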